4. STUDY DESIGN

4.1 OVERALL DESIGN

An overview of the study design is provided in Section [1.2](#).

Study BP42698 is a 3-parallel arm (two dose levels of RO7049665 versus placebo), randomized, placebo-controlled, double-blind, event-driven, phase 2 study to assess efficacy of RO7049665 over placebo in patients with AIH in stable biochemical remission.

Two dose levels will be assessed, 3.5 mg RO7049665 (SC, Q2W) and 7.5 mg RO7049665 (SC, Q2W) and matching placebo.

This is an event-driven study, which means that participants stay in the study and on treatment until the participant experiences an event, the necessary number of events is reached, the participant stops for other reasons or withdraws consent, or the study ends.

All participants in the study will have been diagnosed with AIH previously and will have responded well to treatment with CCSs \pm NSIs. It will be the first attempt to taper out CCS completely *within the last 3 years* (see inclusion criteria Section [5.1](#)). At study entry, the disease status of the participants should allow for a stepwise removal of all

immunosuppressive treatment according to *local guidelines or practice*. If no local guidelines exist, EASL guidelines should be applied (EASL 2015: “Treatment should be continued for at least three years and for at least 24 months after complete normalisation of serum transaminases and IgG levels (biochemical remission). [...] In patients with continued histological disease activity (HAI >3), immunosuppressive treatment should not be discontinued, as relapse is almost certain to occur. [...] A trial of treatment withdrawal should be undertaken by stepwise reduction of immunosuppressive agents, and patients monitored closely.”). Participants will start with study treatment on Day 1 and start tapering CCS use from Day 8 onwards (see tapering schedule, Section 1.3, Table 3) to allow for complete CCS withdrawal within a maximum of 12 weeks, depending on the starting dose. Last dose of NSIs, if any, will be taken on Day –1.

Randomization in a 1:1:1 fashion will occur after patient eligibility is confirmed and before the first dose of study treatment is administered. Randomization will be stratified by equivalent prednisolone dose (≤ 7.5 mg daily versus > 7.5 mg daily or dual therapy [CCS any dose, plus NSI]).

The study is powered to detect a statistically significant difference between one treatment arm and placebo with a sample size of total 84 participants or 28 participants per arm after a total of 45 events are observed (see Section 9.2).

Two interim analyses are planned. The first is planned for futility once 25% of events (i.e., 12 events) are observed. The second interim analysis for efficacy and futility is planned once 50% of events (i.e., 23 events) are observed.

4.1.1 Length of the Study

The study is anticipated to run for approximately 25 months (i.e., 19 months’ recruitment and 6 months’ follow-up), until the necessary number of events is observed. If recruitment and/or the event rate is faster or slower, then the duration of the study could be longer or shorter. It is not possible to estimate the duration of the study for an individual patient as this is an event-driven study; the occurrence of an event cannot be reliably estimated for an individual patient.

Participants will be monitored for at least one hour in the clinical research unit *or at home* after receipt of the first doses administered and receive a follow-up call 8-24 hours postdose *from the site*. If the study treatment is administered at the patient’s home, the nurse will stay for an hour after the administration. To ensure appropriate safety monitoring, the participants will receive the first study treatment injections at the clinical research unit.

Study periods are divided as follows:

- Screening: Up to 28 days.
- Treatment period: Day 1 to relapse or final number of events is observed.

- Safety follow-up: 4 weeks after last administration of study treatment.
- End of study visit: Follow-up visit 28 days after last dose of study treatment. In the event that a participant is enrolled into an open-label extension (OLE) study, the follow-up visit will not apply and the last visit within the treatment period will be considered as the end of study visit.

4.1.2 Stopping-rules Criteria

The study will stop if either of the interim analyses recommends stopping for success. If any interim recommends stopping for futility, the Sponsor's project team will make the actual decision whether to stop or continue the study. This process is mandated by the binding nature of the success boundary and the non-binding nature of the futility boundary defined in Section 9.2. Reasons for continuing the study after a futility recommendation could include, but are not limited to, an efficacy effect that is smaller than assumed in the sample size calculation but still of clinical relevance, or evidence of potential benefit not considered in the primary efficacy analysis.

The dosing in the study will be suspended if any of the conditions below occur in participants treated with RO7049665:

- Clinically manifest secondary (reactive) hypereosinophilia (HER) in > 3 participants.
- Grade 3 hypersensitivity reaction (as per National Cancer Institute Common Terminology Criteria for Adverse Events [NCI-CTCAE] v. 5.0) in > 1 participant considered related to RO7049665.
- Local ISRs leading to treatment discontinuation in > 5 participants, considered related to RO7049665.
- ADA with neutralizing potential against endogenous IL-2 in ≥ 1 participant.
- Other findings (e.g., presence of clinically manifest safety findings in treatment arms typically associated with therapeutic IL-2 doses as per aldesleukin label, other AEs or lab abnormalities) that, at the joint discretion of the Sponsor's lead clinical scientist and safety science leader, the Sponsor's IMC and the Investigators, indicate that dosing should be stopped.

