5000	5	46.5 (27.4)	12.00 (12.00-24.00)	2831 (26.9)	1.77 (26.9)	331 (25.6)	130 (18)
7500	6	68.7 (85.6)	12.00 (5.98-12.00)	5266 (55.4)	1.42 (55.4)	281 (62.4)	137 (9.3)

AUC_{inf} = area under the serum concentration-time curve extrapolated to infinity; C_{max} = maximum serum concentration observed; CL/F = apparent clearance; ND = not determined;

T_{1/2} = terminal elimination half-life; T_{max} = time to maximum concentration; Vz/F = apparent volume of distribution.

^a Median (Min–Max).

PD data showed that RO7049665 expanded the T_{reg}-cell pool, thereby delivering proof of pharmacology in a healthy population. The T_{reg} expansion was dose-dependent, and reached an absolute increase of approximately 200 cells/µL at the maximum tested dose of 7500 µg, ranging from 123 cells/µL to 297 cells/µL. This represented a mean fold increase of 5.9 (2.9-7.6) from baseline. The peak was, on average, reached on Day 8, following a drop at 24 hours postdose, and T_{reg} levels were back to baseline values at Follow-up (Day 57). Overall, the estimated therapeutic range of T_{reg} was achieved with the doses of 2200 µg, 5000 µg, and 7500 µg, eliciting a mean increase of 2-fold, 4-fold, and 6-fold, respectively, as compared with baseline.

There was no expansion of NK cells in any dose group, and no significant trends observed in eosinophils. There was no obvious effect on T_{eff} at doses up to 2200 µg. A possible weak trend for increase in T_{eff} count occurred with doses of 5000 µg and 7500 µg, with mean change from baseline on Day 12 reaching up to 1.5-fold increase from baseline.

In the ongoing study WP40161, to date, multiple doses of 3.5 mg and 7.5 mg (to date, 3 cohorts) were safe and well tolerated, and induced dose-dependent T_{reg} expansions up to 5-fold (mean at the highest dose of 7.5 mg) those of baseline.

The most frequently reported AEs were injection site reactions (ISR) and eosinophilia. The majority of AEs reported were mild or moderate (Grade 1 or 2) in intensity except for

a low number of events of severe (Grade 3) intensity, including anemia, eosinophilia and hyperkalemia. No events of CLS were reported. Hypersensitivity and injection related reactions (IRR) have been reported. All events resolved without sequelae or are ongoing. There were no deaths reported to date.

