Study BP42698 is the first study involving dosing of RO7049665 in participants with AIH. At the time of the commencement of Study BP42698, the safety data in healthy volunteers from the EIH Study WP39826 are available, as are some preliminary data from the MAD study WP40161 in participants with UC (see Section 2.2.2.1). Potential risks have been defined on the basis of clinical experience in healthy volunteers and preliminary data from patients with UC, non-clinical pharmacology and toxicology data in the relevant animal species, and theoretical risks based on expected PD effects and the safety profile of aldesleukin. The doses planned for Arm 1 (3.5 mg) and Arm 2 (7.5 mg) are being assessed in study WP40161.

The eligibility criteria, design, and procedures adopted are considered appropriate for the safe conduct of the study. Participants will be closely monitored for safety.

Identified potential risks and plans for their mitigation are as follows:

- Excessive interleukin-2 effects
- Hypersensitivity
- ADA formation
- Increased T_{regs} causing immunosuppression
- ISRs
- Heart rate and 12-lead ECG parameters

For further details, see the [RO7049665 Investigator Brochure](#).

Safety monitoring and risk mitigation measures listed below will be implemented:

- Participants will be monitored closely throughout the study for their well-being by a phone call following the administration of each dose.
- Assessments of ADA development, their neutralizing capability and the impact on continued dosing are scheduled throughout the study.
 - Study level stopping criteria relating to hypersensitivity reactions and development of neutralizing antibodies to endogenous human IL-2 (see Section 4.1.3).
 - Signs and symptoms of autoimmune diseases will be monitored and treated according to standard of care.
- Procedure-related Risks

The procedures performed include an optional liver biopsy at 6 months to assess the inflammation and gain insight on immune cells in the liver tissue, SC injections, and blood draws. The risks associated with liver biopsies include bleeding, pain, and injury to adjacent organs and infection. SC injections may produce a local inflammatory reaction, which can range from a slight irritation to infection or possible necrosis. The risks associated with blood draws include hematoma, and rarely injury to neurovascular structures.

- Risks Related to Concomitant Medications

Risks of CCS and RO7049665 Adjunctive Therapy

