Furthermore, following the outbreak of coronavirus (COVID-19 or SARS CoV2, declared as a global pandemic by the World Health Organization [WHO]), the Sponsor will provide the sites with guidance on the reporting of AEs and the capturing of COVID-19 test result data. There is currently no identified impact of COVID-19 on the data of the ongoing study WP40161, or on the known benefit-risk profile of RO7049665.

Overall, the expected benefits of RO7049665 in the treatment of autoimmune conditions are greater than the expected risks. The level of risk for participants with AIH is considered acceptable as it is mitigated by careful monitoring, careful dose selection,

and study-stopping criteria (Section 4.1.2 and Section 4.1.3). More detailed information about the known and expected benefits in the context of potential risks and reasonably expected AEs of RO7049665 is provided in the IB.

3. **OBJECTIVES, ENDPOINTS, AND ESTIMANDS**

The objectives and corresponding endpoints are provided in Table 5.

Table 5 Objectives and Endpoints

Objectives	Endpoints
Primary	

 To evaluate the effect of RO7049665 on time to relapse following forced CCS tapering as measured by the hazard ratio between 7.5 mg RO7049665 and placebo. 	
 Time to relapse from randomization.
Secondary	

 To assess changes in alanine aminotransferase (ALT), aspartate aminotransferase (AST), and IgG over time and by dose. 	
 ALT, AST, and IgG (for both Δ, absolute and relative [ULN]) over time.

 To evaluate the effect of RO7049665 on time to relapse following forced CCS tapering as measured by the hazard ratio between 3.5 mg RO7049665 and placebo. 	
 Time to relapse from randomization.

 To evaluate the safety and tolerability of RO7049665 in participants with AIH. 	
 Incidence and severity of adverse events. Changes in vital signs, physical examination, ECG parameters, and safety laboratory parameters. ADA emergence and neutralizing potential.

Tertiary/Exploratory	

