4.1.3 Individual Stopping Criteria

Dosing will be stopped in a given individual participant if the following circumstances occur:

- Grade 3 or greater severe AE or SAE considered related to study treatment, including but not limited to:
 - Hypersensitivity reaction which is considered related to study treatment and believed to pose an unacceptable risk if the dose is repeated.
 - CLS including severe, clinically significant respiratory distress syndrome, edema, effusions, or decrease in blood pressure (BP).

- Grade 3 or higher injection-related reaction (i.e., cytokine release syndrome and severe, acute influenza-like syndrome).
- Disease relapse signifying study treatment failure (See Section 7).
- Other findings that, at the discretion of the Investigator, indicate that dosing should be stopped.

Study closure information is provided in Section 4, [Appendix 1](#).

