8.3.6 Non-Serious Adverse Events of Special Interest

NSAESIs are required to be reported by the Investigator to the Sponsor immediately (i.e., no more than 24 hours after learning of the event; see [Appendix 2](#) for reporting instructions).

NSAESIs for this study include the following:

- Cases of an elevated ALT or AST in combination with either an elevated bilirubin or clinical jaundice, as defined in [Appendix 3](#).
- Suspected transmission of an infectious agent by the study treatment, as defined below:

Any organism, virus, or infectious particle (e.g., prion protein transmitting transmissible spongiform encephalopathy), pathogenic or non-pathogenic, is considered an infectious agent. A transmission of an infectious agent may be suspected from clinical symptoms or laboratory findings that indicate an infection in a participant exposed to a medicinal product. This term applies only when a contamination of the study treatment is suspected.

- NCI CTCAE (v5.0) \geq Grade 2 IRRs and any hypersensitivity.

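### The study-level suspension trigger in Section 4.1.2 counts only Grade 3 related hypersensitivity, so read literally Grade 4 and 5 reactions do not count

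*Combined protocol and SAP*

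**What the plan says.** Section 4.1.2 introduces its list of triggers with mandatory wording: "The dosing in the study will be suspended if any of the conditions below occur in participants treated with RO7049665". The hypersensitivity bullet is "Grade 3 hypersensitivity reaction (as per National Cancer Institute Common Terminology Criteria for Adverse Events [NCI-CTCAE] v. 5.0) in > 1 participant", limited to reactions considered related to RO7049665. It carries no qualifier such as *or greater*, *or higher* or ≥.

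Section 4.1.3, on stopping dosing in one participant, is open-ended. Its first criterion is "Grade 3 or greater severe AE or SAE considered related to study treatment, including but not limited to", with related hypersensitivity among the listed examples, and it also names a "Grade 3 or higher injection-related reaction".

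Section 2.3 lists among its risk mitigation measures "Study level stopping criteria relating to hypersensitivity reactions and development of neutralizing antibodies to endogenous human IL-2", but refers the reader to Section 4.1.3 for them. The study-level criteria are in Section 4.1.2.

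**The concern.** A counted safety trigger should respond at least as strongly to worse events. This one does not: the less severe pattern forces a suspension and the more severe pattern leaves the bullet unmet. Above Grade 3, a study-wide suspension would rest on judgement, where the protocol otherwise commits to a fixed count.

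Section 2.3 relies on the criteria in Sections 4.1.2 and 4.1.3 as part of its reason for calling the risk acceptable, in the first study of this drug in autoimmune hepatitis. The event type is not hypothetical. For the ongoing ulcerative colitis study, Section 2.2.2.1 says "Hypersensitivity and injection related reactions (IRR) have been reported", without giving the grade of those reactions. At stake is the automatic protection of participants still on dosing; no efficacy inference is involved.

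**Working it through.** The plan states no operating characteristic for this trigger, so there is no figure to reproduce. The check is a comparison of texts followed by a count.

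**1. Are Grades 4 and 5 separate from Grade 3?** Yes. The severity table in Appendix 2, Section 3.1 defines Grade 4 as life-threatening and Grade 5 as death, each as its own grade.

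**2. How does the document write open-ended grades elsewhere?**

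| Place | Subject | Grade wording |
|---|---|---|
| 4.1.2 | Study-level hypersensitivity trigger | Grade 3, no qualifier |
| 4.1.3 | Related AE or SAE, individual stop | Grade 3 or greater |
| 4.1.3 | Injection-related reaction (IRR), individual stop | Grade 3 or higher |
| 8.3.6 | IRR as event of special interest | ≥ Grade 2 |
| 8.3.7 | IRR sampling | Grade ≥ 2 |
| 1.3, Table 1, footnote F | IRR sampling | Grade 2 or above |

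Where an open-ended grade is meant, the text says so. The contrast with Section 4.1.3 is not perfectly like for like: there the open-ended grade governs related AEs and SAEs in general, and the hypersensitivity example adds a judgement about the risk of repeating the dose. The difference in grade wording remains.

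**3. Does another trigger in Section 4.1.2 cover the gap?** The remaining specific triggers concern hypereosinophilia, local injection-site reactions and neutralizing antibodies. Only the bullet on other findings could reach Grade 4 or 5 hypersensitivity, and it needs the joint discretion of the sponsor's lead clinical scientist and safety science leader, the IMC and the investigators.

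**4. Count by case.** Take related reactions in two participants. The literal count is the number with grade = 3; the open-ended count is the number with grade ≥ 3. Dosing is suspended if the count exceeds 1.

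| Grades | Literal count | Suspend? | Open-ended count | Suspend? |
|---|---|---|---|---|
| 3, 3 | 2 | yes | 2 | yes |
| 3, 4 | 1 | no | 2 | yes |
| 3, 5 | 1 | no | 2 | yes |
| 4, 4 | 0 | no | 2 | yes |
| 4, 5 | 0 | no | 2 | yes |
| 5, 5 | 0 | no | 2 | yes |

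The literal rule fires in 1 of 6 cases and the open-ended rule in 6 of 6. The cases are not equally likely, so 1 in 6 is not a failure rate.

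**5. Illustration under assumed rates.** The document gives no rate of related Grade 3 to 5 hypersensitivity; the rates below are assumptions. With 28 participants per arm (synopsis) and two active arms, n = 2 × 28 = 56. Let p be the probability that a participant has a counted reaction, with participants independent. Then P(X ≥ 2) = 1 − (1 − p)^56 − 56·p·(1 − p)^55. The literal rule uses p = Grade 3 rate; the open-ended rule uses p = Grade 3 rate + Grade 4–5 rate.

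| Assumed Grade 3 | Assumed Grade 4–5 | Literal | Open-ended |
|---|---|---|---|
| 2% | 0% | 0.309 | 0.309 |
| 2% | 1% | 0.309 | 0.504 |
| 2% | 2% | 0.309 | 0.661 |
| 1% | 2% | 0.108 | 0.504 |
| 0% | 5% | 0 | 0.777 |

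The two rules coincide when no Grade 4–5 reaction occurs. Otherwise the literal trigger is insensitive to the Grade 4–5 rate. The conclusion does not depend on these figures.

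**The case against.** The strongest reply is that this is a drafting slip nobody would act on. Harm would require the sponsor, the IMC and the investigators to suspend for two Grade 3 reactions and yet hold that two life-threatening ones do not count.

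Several other controls apply:

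- Section 4.1.3 stops dosing in the affected participant when the event is related.
- Section 8.3.6 requires reporting within 24 hours of ≥ "Grade 2 IRRs and any hypersensitivity".
- Appendix 2 sends Grade 4 and 5 events through SAE reporting and commits the sponsor to prompt evaluation of each SAE.
- The IMC reviews safety data.
- The bullet on other findings in Section 4.1.2 allows suspension.
- Appendix 1, Section 4 lets the sponsor terminate the study at any time, names the incidence or severity of adverse events as a reason, and provides for a hold.

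There is also no reported precedent. Section 2.2.2.1 describes mostly Grade 1 or 2 events in the colitis study with a few at Grade 3 and no deaths, and no serious adverse events in healthy volunteers.

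All of this stands, and it keeps the point minor. It shows that detection and the power to act are intact. It does not restore the fixed count, and the intended reading is not written anywhere for the study-level rule. The wrong cross-reference in Section 2.3 is a separate slip of little weight alone, since the two sections are adjacent.

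**Conclusion.** The concern holds. The hypersensitivity trigger in Section 4.1.2 is wrong as written: taken literally, it omits the reactions more severe than those it counts. The loss is confined to the automatic counted suspension for related Grade 4 and 5 hypersensitivity. This rests on a literal reading; the intent was probably open-ended. How often it would matter cannot be estimated from the document. Confidence is high about the wording and makes no claim about the likelihood of harm. It should be corrected, but it does not threaten the trial's inference.

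**What to change.** In the hypersensitivity bullet of Section 4.1.2, insert *or greater* after Grade 3, leaving the count and the relatedness condition unchanged. In Section 2.3, point the reference for the study-level criteria to Section 4.1.2. Check that the IMC charter, which is not part of the document, uses the same grade wording.

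The cost is two words and one cross-reference at the next amendment, plus the charter check. The only downside is a slightly higher chance of a dosing suspension, and only where a related Grade 4 or 5 reaction contributes to the count. Sample size, alpha and power do not change.

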4.1.3 Individual Stopping Criteria

Dosing will be stopped in a given individual participant if the following circumstances occur:

- Grade 3 or greater severe AE or SAE considered related to study treatment, including but not limited to:
 - Hypersensitivity reaction which is considered related to study treatment and believed to pose an unacceptable risk if the dose is repeated.
 - CLS including severe, clinically significant respiratory distress syndrome, edema, effusions, or decrease in blood pressure (BP).

- Grade 3 or higher injection-related reaction (i.e., cytokine release syndrome and severe, acute influenza-like syndrome).
- Disease relapse signifying study treatment failure (See Section 7).
- Other findings that, at the discretion of the Investigator, indicate that dosing should be stopped.

Study closure information is provided in Section 4, [Appendix 1](#).

4.1.4 Communication Strategy

The Sponsor and Investigators will be in regular contact throughout the study by email/telephone/fax, as per normal interactions during the conduct of a clinical study, and the Sponsor will arrange regular teleconferences and meetings to discuss study status.

The Sponsor will be available 24 hours a day to discuss any medical or study-related issues that may arise during the conduct of this study.

